## **5. STUDY POPULATION:**

The study population includes female sex workers (FSW) and adolescent girls and young women (AGYW) who will participate in the TB HIV Care programme over a one year period (12-months) across multiple sites starting at the launch of the campaign. Overall, since programme inception, TB

HIV Care has implemented PrEP services for women in 17 sites across 6 provinces. Currently 13 sites are actively implementing PrEP programming in 10 districts across 4 provinces and will contribute to the CRT aggregate level data: OR Tambo, Eastern Cape (AGYW & FSW); Zululand, KZN (AGYW); uThukela, KZN (AGYW); uMgungundlovu, KZN (AGYW & FSW); eThekwi, KZN (AGYW & FSW); Ehlazeni, Mpumalanga (FSW); Gert Sibande, Mpumalanga (FSW); Nkangala, Mpumalanga (FSW), [name], North West Province (FSW); and Ngaka Modiri Molema, North West Province (FSW). Here, participation is defined as receiving  $\geq 1$  of the following HIV prevention services offered to FSW and AGYW by TB HIV Care: STI screening and/or treatment, pregnancy testing, HIV testing, or any other service that would result in having a health screening form on file. All clients seen by TB HIV Care are assigned to HIV acquisition risk groups (FSW, AGYW, or others) the first time they are seen based on risks reported on a standardized intake form. Women screening positive for HIV on their first encounter with the programme during the study period will be excluded.

The time period of interest will be 12-months. We anticipate the social media campaign to launch in February 2022, in which case the study period would be February 1, 2022-January 31, 2023. The one year of follow-up will begin at the time of campaign launch.

#### *A. Inclusion Criteria*

**For active enrollment for cross-sectional survey:** Participants will be recruited during programmatic activities led by TB HIV Care. Cisgender women and adolescent girls (15+ years) who are eligible for PrEP per TB HIV Care programmatic criteria: HIV negative; AND engaged in sex work (18+ years) OR transactional sex OR sex with multiple partners OR who have a partner who has multiple partners OR have a partner who is known or suspected to be HIV positive); AND individuals must also be current TB HIV Care HIV prevention programme users (including HIV prevention messaging, condoms, HIV/STI testing and/or PrEP).

**For passive enrollment using programme data:** Analyses using de-identified, aggregate programmatic data will utilize data from cisgender adolescent girls and young women (15-24 years) engaged in the AGYW programme and cisgender FSW women (18+ years), who are eligible for PrEP per TB HIV Care programmatic criteria (HIV negative, engaged in sex work or transactional sex or sex with multiple partners or who have a partner who has multiple partners or is known or suspected to be HIV positive); individuals must also be current TB HIV Care HIV prevention programme users (including HIV prevention messaging, condoms, HIV/STI testing and/or PrEP). Programmatic data will be utilized in an aggregate, de-identified manner, similar to what is reported to the Department of Health and program donors (PEPFAR/CDC).

#### *B. Exclusion Criteria:*

**For active enrollment for cross-sectional survey:** Not eligible for PrEP (no risk factors identified in programmatic screening).

**For passive enrollment using programme data:** Not eligible for PrEP (no risk factors identified in programmatic screening).

#### *C. Selection of the Study Population:*

**For active enrollment for cross-sectional survey:** A sample of TB HIV Care HIV prevention program users (individuals the HIV prevention team engages with, including but not limited to offering PrEP, independent of uptake) will be approached by research assistants with quantitative interviewing experience independently hired through the study.

*Pre-intervention launch:* First, we will randomly sample 6 programme districts (3 in Arm 1 – standard of care areas, and 3 in Arm 2 intervention areas). Next, within each selected district, we will work closely with the programme site(s). Each programme site has one or more HIV prevention/PrEP programme team which operates at drop-in centres or at mobile vans operating at various community-based venues. Each programme site has a schedule of venues that they visit each day. During the one-month active enrollment period, these schedules will be used to randomly select two implementation teams to accompany each work-day (each day we will sample one team without replacement and then sample a second team; the next day all teams will be eligible for sampling again). One research assistant will accompany each team (in the event that there is only one programme team, both research assistants will accompany that team). Based on the programme teams randomly selected on a given day, we will accompany the team in their programmatic activities. During these visits, the research assistant will consecutively approach women at the site (starting with the order of arrival), explaining the study, screening for eligibility and offering a brief 20-30 minute survey to eligible women and adolescent girls engaging with the service. We will recruit up to 4 women and girls per day per site (8 if there is only one team for both research assistants to accompany). This will ensure a wider representation of women and girls from sites across the district. Recruitment will last an estimated 4 weeks (~25 women and girls per week per site will be recruited, which across two research assistants is roughly 2-3 interviews per day, with a maximum of 4 allowed). Each site will conduct 100 cross-sectional interviews during this one-month period; enrollment in some cases may be slightly faster or slower than one-month, but we anticipate one-month will be on average how long it will take.

*Post-intervention:* Using the previously sampled districts, we will repeat the approach of randomly selecting teams to accompany after 1-year of intervention activities. This post-intervention survey will be identical in approach to the first survey (n=100 participants per site), although a few additional questions will be added to the post-intervention to assess exposure to the intervention. Participants who completed the first survey will not be intentionally recruited for the follow-on post-intervention survey, but if present and systematically approached on the day of enrollment, individuals will not be excluded if they participated in the prior round of research.

*Pre and post-intervention survey:* The survey will collect minimal individual behavior data, and is mainly intended to assess PrEP knowledge and attitudes, exposure to PrEP promotion events and the social media campaign, as well as the woman or adolescent girl's views on partner, family and peer perceptions of PrEP. Interviews will be conducted cross-sectionally at two time points (serial cross-sectional interviews with programme users). Following screening and the informed consent/assent process, the trained research assistants will administer the survey to study participants on a tablet, reading each question aloud and recording all participant responses. Overall, 600 women and adolescent girls (300 in the standard of care and 300 in the intervention sites) will be enrolled pre-intervention and 600 women and adolescent girls (300 in the standard of care and 300 in the intervention sites) will be enrolled post-intervention, totaling 1,200 participants across the sites and the two time periods.

**For passive enrollment using programme data:** No individual human subjects will be recruited for this element of the study. Rather than individually target programme users with the enhancements to understand their impact, these are strategies that are attempting to change the

norms around PrEP within communities and social spaces which cannot be individually randomized. Thus, we are randomizing clusters (sites) to receive the package and it will be offered routinely throughout. Women engaging with the TB HIV Care programme may or may not notice or be impacted by the intervention, however each has the potential to be reached by it if they are in the programme area. Routinely collected, aggregate programme data will be used to assess the proportion of FSW and AGYW programme users within the TB HIV Care PrEP programme who initiated PrEP among all eligible women to whom it was offered per programme logs during the 12-month period of the PrEP social influence campaign (CRT).

**For passive enrollment using social media metrics:** Through Facebook Ad Manager (and Instagram or other platforms if relevant), we will receive analytic data to assess our ad metrics, including: # times each ad was viewed overall and by an individual, # times someone clicked on each ad, and the click-through rate metric which tells you the percentage of people who click an ad out of all the people who saw the ad; we will also assess the number of website/Facebook page visits, video views and appointments made. Quotes may be collected from posts in the study's public facing Facebook group to be used anonymously in analyses. This will be made clear in the study's Facebook group description, and no names will be linked to quotes. No quotes will be collected from any users' posts outside of the study public Facebook group; for example private messages sent through Facebook messenger will be categorized based on their general content as process indicators (e.g. informational questions, access questions, questions pertaining to personal risk, etc. ), but any direct quotes will be excluded from analysis.

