#### **4. STUDY DESIGN:**

This grant combines evaluation of ongoing PrEP programme implementation (previous work) with modified, programme informed implementation strategies for testing through two short-duration cluster randomized trials (CRTs). Specifically, this study protocol is focused on PrEP programme optimization through modifying the implementation strategies of ongoing programmatic activities by adjusting the delivery modalities and actors promoting PrEP within the community. The effect of these modifications on PrEP uptake (primary outcome) and continuation (secondary outcome) will be tested using an initial CRT. A second CRT focused primarily on PrEP continuation (retention) will be included in a separate, future protocol.

TB HIV Care is a South African non-profit organization that works directly with the Department of Health as the country's largest PrEP provider for AGYW and FSW. TB HIV Care has initiated over 33,000 women at high risk for HIV infection on PrEP, and has 13 active sites as of 2021. Of note, these are two PrEP programmes that are run by TB HIV Care (8 of the 13 active sites are part of the FSW programme and 5 of the 13 active sites are part of the AGYW programme). **The proposed study design leverages a cluster randomized trial design as some intervention components may not be feasibly randomized at the individual-level (e.g. PrEP peer ambassadors operating within venues/community locations, community mobilization and social media ads).** This trial is feasible given the short duration of the outcomes measured (PrEP uptake and 1- and 4-month PrEP persistence) and utilization of routine programme data for primary outcome ascertainment, and the testing is an adaptation of existing interventions. Based on the programme team's experience and PrEP barriers literature, this first CRT will focus on generating sustained PrEP demand, but also destigmatizing PrEP within young women's social environments (e.g. family, friends, partners). **CRT1 is described within this application.** The second CRT will likely optimize peer support mechanisms during the early days of PrEP use, but this will be refined in late 2022 based on the programme's input and a separate protocol will be submitted surrounding CRT2.

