**Cross-sectional survey:** In order to assess the penetration of exposure to the intervention and thus yield insights into the mechanism of intervention effect (or lack thereof), we are assessing changes in PrEP knowledge and community attitudes over time. Given that awareness to PrEP and attitudes may change over time independent of the intervention, we have included both intervention and control sites pre- and post- intervention in order to compare differences in awareness and attitudes over time between the intervention and control sites. Cross-sectional surveys will be administered across 3 intervention and 3 control sites pre- and post-CRT implementation. With 100 surveys being conducted per site per timepoint, we will collect a total of 1200 survey responses across the 6 selected sites (600 pre-intervention and 600 post-intervention). When selecting the 6 sites for survey implementation, programme type (FSW vs. AGYW vs. both) will be accounted for and from there a random sample will be drawn. With 100 women included per site, there will be a sufficient number of women to account for heterogeneity across sites and will ensure sufficient representation across both intervention and control sites, but will also allow for 300 combined FSW/AGYW before and 300 combined FSW/AGYW after intervention in the intervention arms, which will allow for further assessment of the impact of the additional layered strategies (PrEP champions and community mobilization) on modifying the effect of the social media campaign on PrEP uptake.

**Social media metrics:** No sampling plan needed; these will be process indicators used to evaluate engagement with the social media campaign (intervention activities).

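### The survey quota of 100 interviews should be stated per district, and the daily team draw in two-programme districts should be stratified by programme (minor point, secondary outcome)

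*Combined protocol and SAP*

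**What the plan says.** The survey is repeated in the same six districts before and after the intervention, three per arm. The relevant statements are these.

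- **Sites and districts.** Section 5: "Currently 13 sites are actively implementing PrEP programming in 10 districts across 4 provinces". Its list marks three districts (OR Tambo, uMgungundlovu and eThekwi) as carrying both programmes. Section 4 agrees: "8 of the 13 active sites are part of the FSW programme", and the other five belong to the AGYW programme.
- **Quota.** Section 5.C draws districts, refers to the programme site or sites within each, gives each programme site one or more teams, and then states: "Each site will conduct 100 cross-sectional interviews during this one-month period".
- **Totals.** Later in Section 5.C: "Overall, 600 women and adolescent girls (300 in the standard of care and 300 in the intervention sites) will be enrolled pre-intervention", with the same number after the intervention. Section 7.B repeats 100 per site, six sites and 1,200 in all. Section 7.A treats district and site as the same unit.
- **District selection.** Section 5.C describes a plain random sample of districts within arm. Section 7.B says that "programme type (FSW vs. AGYW vs. both) will be accounted for and from there a random sample will be drawn", without saying how.
- **Team selection.** Section 5.C: "these schedules will be used to randomly select two implementation teams to accompany each work-day". No programme quota or stratum is given for this draw.
- **Analysis.** Section 7.C models period, arm and their interaction in suitable regression models. It names no programme-type term for the survey.

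**The concern.** Within Section 5.C a programme site is a unit inside a district, and the quota is attached to the site. In a two-programme district that means 200 interviews, which does not fit the stated totals. Field staff and analysts need a single definition.

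Once the quota is taken as per district, a second gap appears. In a mixed district the two daily teams are drawn from all teams without regard to programme. Selecting districts by programme type and returning to the same districts fixes the mix between districts, but not inside a mixed one. FSW are aged 18 and over and AGYW are 15 to 24 (Section 5.A), so the two groups may well answer knowledge and attitude items differently. The two rounds interview largely different women, and a shift in the mix of a mixed district would appear as a change over time. With three districts per arm, each district carries a third of its arm's estimate.

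**Working it through.** **1. The plan's own total.** 6 sites × 100 = 600 per round; × 2 rounds = 1,200; 3 × 100 = 300 per arm. This reproduces exactly if site means district.

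**2. The literal programme-site reading.** The Section 5 list gives 5 FSW-only, 2 AGYW-only and 3 mixed districts: 5 + 2 + 3 × 2 = 13 sites (8 FSW, 5 AGYW), as stated. With k mixed districts among the six, interviews per round = 100 × (6 + k):

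| k | Per round | Probability, plain random draw |
|---|---|---|
| 0 | 600 | 3.3% |
| 1 | 700 | 30% |
| 2 | 800 | 50% |
| 3 | 900 | 16.7% |

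The mean is 600 + 100 × 3 × 6/10 = 780. These probabilities ignore whatever use Section 7.B makes of programme type, so they only illustrate the literal rule.

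**3. Field pace.** 25 per week × 4 weeks = 100, or 2.5 per research assistant per day. The cap is 2 × 4 × 20 days = 160. If one pair of assistants covers a district (assumption), 200 interviews would not fit in four weeks. This also favours the per-district reading.

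**4. Mix within a mixed district, per-district reading.** The documents give no team counts. Assume 20 work-days, two teams a day and equal interviews per team. With T teams, a proportion p of them FSW, the daily number of FSW teams drawn has variance 2p(1−p)(T−2)/(T−1). The SD of the FSW share over a round is √(20 × variance)/40.

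| FSW + AGYW teams | SD per round | SD of pre-post change (× √2) |
|---|---|---|
| 1 + 1 | 0 | 0 |
| 2 + 2 | √(20 × 0.333)/40 = 6.5 points | 9.1 points |
| 3 + 3 | √(20 × 0.4)/40 = 7.1 points | 10.0 points |

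For comparison, a simple random sample of 100 women from an evenly mixed population has SD √(0.25/100) = 5 points.

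**5. Effect on the difference-in-differences.** Assume the programmes differ by 30 points on an item. With 2 + 2 teams, the spurious change in one mixed district has SD 0.30 × 9.1 = 2.7 points. With k independent mixed districts, each weighted one third in its arm, the SD is 2.7 × √k / 3: 0.9 points (k = 1), 1.3 (k = 2), 1.6 (k = 3).

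**6. Benchmark.** At p = 0.5 with 300 per arm and round, ignoring clustering, SE = √(4 × 0.25/300) = 5.8 points. Adding 1.6 in quadrature gives √(5.8² + 1.6²) = 6.0, a rise of less than 4%.

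**7. Systematic shift.** If a mixed district went from 2 + 2 teams to 3 FSW + 2 AGYW teams, the expected FSW share would move from 50% to 60%. At a 30-point gap that is 0.30 × 10 = 3 points in the district and 1 point in its arm. Repeated draws do not average this out.

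**8. Interviews affected.** At most 3 × 100 = 300 of 600 per round. In single-programme districts the programme is set by the district.

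**The case against.** A reader might infer that the survey will overrun to as many as 900 interviews per round. The documents do not support that. The totals of 600 and 300 are explicit, Section 7.B ties the quota to six sites, Section 10.E again speaks of six selected sites, and Section 7.A equates district and site. What stands is that one word carries two meanings.

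A reader might also infer that the FSW/AGYW mix of the whole survey is left to chance. That does not stand either. Seven of the ten districts have a single programme, the same districts are used in both rounds, and programme type is to be accounted for in choosing them. Chance enters only inside mixed districts.

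The size can be challenged too. The random component is close to ordinary sampling variation, depends on assumed team counts and vanishes with one team per programme. The systematic route needs team numbers to change. The documents do not say that they will, although Section 2 expects the programme to go on expanding. All of this stands, and it makes the point minor.

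Two objections to the remedy carry less weight. Teams might serve both programmes, since Section 2 notes substantial overlap; but Section 5.C places teams within programme sites, and Section 4 assigns each site to one programme. A fixed split may not mirror actual programme users; that is true, and choosing the split from programme volumes or weighting deals with it.

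**Conclusion.** The point holds as a minor one on a secondary outcome. The definition of site must be made consistent, and Sections 5.C and 7.B should agree on how programme type enters the choice of districts. Under the per-district reading, the team draw leaves the FSW/AGYW mix uncontrolled in mixed districts. The resulting noise has an SD of about 0.9 to 1.6 points on the difference-in-differences, plus a possible systematic shift if team numbers change between rounds.

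These sizes rest on a 30-point gap between programmes, two teams per programme, 20 work-days and equal interviews per team, none of which is fully given in the documents. The primary outcome comes from programme data and is untouched. The case for acting is that the remedy is nearly free, not that the survey is at serious risk.

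**What to change.** 1. In Section 5.C, state the quota as 100 interviews per district per round, and use separate terms for district, programme site and venue throughout.
2. Make Sections 5.C and 7.B give the same account of how programme type enters the selection of the six districts.
3. In mixed districts, stratify the daily draw: one FSW team and one AGYW team, one per research assistant. Keep the same FSW:AGYW split in both rounds. An even split needs 2.5 interviews × 20 days = 50 per assistant, which is the pace already planned.
4. Record programme type for each interview, and include it as a term in the difference-in-differences model in Section 7.C. It is already a constraint in the district randomisation (Section 7.A).
5. If an even split would misrepresent programme users, set the split from baseline programme volumes, or weight the results to those volumes.

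The cost is a few sentences, one recorded field and one model term. No extra staff or interviews are needed. The only drawback is the possible mismatch with the user mix, which item 5 handles.

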Arm 2b**	PrEP champions	Within venues served by the FSW and AGYW programs, we will identify and train 1 venue-based PrEP champion per venue who will (a) have completed a 2 day group-based (cross-venue) health information training related to PrEP knowledge, with pre and post testing knowledge assessments to identify knowledge gaps; (b) receive supplies (e.g. a hat, pin and posters, flyers, IEC material) to wear to promote PrEP; (c) facilitate linkage between women interested in PrEP and the TB HIV Care PrEP programme; and (d) receive bi-weekly follow-up support from TB HIV Care to discuss challenges, progress and referrals. A partial day refresher training will be held at 3-months. PrEP champions will be either peers with experience taking PrEP, venue managers or local influencers (e.g. women running shops next to the mobile serving AGYW) that have repeated contact with the women the programme is intended to serve. The final selection of PrEP champions will be made in consultation with the Community Advisory Groups, venues and by the programme who works closely with each of the sites. The PrEP champions will receive a small airtime stipend (R150 per month) to follow-up and provide support to women engaging in PrEP.
Arm 2c**	PrEP community mobilization	A PrEP community mobilization team (2 peers, including one woman and one man) will be recruited within each ward to promote PrEP. The team will present information about PrEP and the PrEP programme at the ward councilors meeting, at Learning Support Agent meetings with parents/guardians, at local events/fairs, community meetings and through engaging men, women and parents across the community through informal conversations. Teams will be wearing branded material and will focus on presenting factual information and decreasing PrEP stigma, and will have received 3 days of training in HIV, PrEP, and health communication and persuasion to promote positive PrEP norms and attitudes within the community, with a 1-day refresher training at 3-months. Each team will focus on promoting PrEP within their own ward over the 6-month period.
Arm 2d**	PrEP champions + PrEP community mobilization	Wards in Arm 2d will receive both of the two additional strategies described above (2b & 2c).

\*10 districts randomized 1:1 across Arms 1 and 2.

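### Both survey rounds sample only women attending the programme, so the difference-in-differences on attitudes is open to bias if the campaign changes who attends in Arm 2

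*Combined protocol and SAP*

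**What the plan says.** **Who is surveyed.** Section 5.A sets a condition of entry to the survey: "individuals must also be current TB HIV Care HIV prevention programme users". Section 5.C defines the frame as "program users (individuals the HIV prevention team engages with, including but not limited to offering PrEP, independent of uptake". Teams are chosen at random each day, and women are approached consecutively in order of arrival. For the second round: "Using the previously sampled districts, we will repeat the approach of randomly selecting teams to accompany after 1-year of intervention activities". The rounds are serial cross-sections. Earlier respondents are neither sought nor excluded.

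**What the intervention does.** Section 4 states that "this first CRT will focus on generating sustained PrEP demand". In Table 1, the champions in Arms 2b and 2d are to "facilitate linkage between women interested in PrEP and the TB HIV Care PrEP programme". Section 5.C and Table 4 count appointments made among the campaign metrics.

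**What the survey is for.** Section 7.B gives the purpose: "In order to assess the penetration of exposure to the intervention and thus yield insights into the mechanism of intervention effect". Section 4 lists differences between arms in knowledge, attitudes and peer influence as secondary outcomes. Section 7.C analyses them by difference-in-differences, with terms for period, arm and their interaction. Section 7.B includes control sites because awareness and attitudes may move without the intervention. Table 4 takes penetration, meaning reach among FSW/AGYW and their families, peers and partners, from the survey.

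**What is recorded.** Sections 5.C and 6 describe knowledge, attitudes, exposure, perceived views of others, minimal behaviour, age and location. Neither mentions when or why a woman first came to the programme. Section 8 says the survey is anonymous with no link-logs.

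**The concern.** A difference-in-differences on repeated cross-sections estimates attitude change only if the mix of respondents would have moved alike in both arms. Here the intervention may itself move the mix, in one arm only. If the campaign draws in women who already favour PrEP, Arm 2 attitudes rise between rounds although no woman has changed her view. If it draws in women new to PrEP, average knowledge could fall and hide a real gain among existing users.

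The survey is the plan's source of evidence on mechanism, and changing community norms is a stated aim in Section 3. As planned, a reader of the results could not tell changed views from changed attendance. Because the survey is anonymous and unlinked, programme records cannot supply the missing information afterwards.

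**Working it through.** **1. The plan's own figures.** 6 sites × 100 × 2 rounds = 1,200 responses, and 3 × 100 = 300 per arm per round. Both agree with Section 7.B. No effect size or power is stated for the survey.

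**2. What the control districts remove.** Let π be the favourable rate among ordinary attenders, with no true attitude change. Let s be the share of Arm 2 second-round respondents who attend because of the campaign, and d the amount by which their favourable rate exceeds π.

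- Arm 2, second round: (1 − s)π + s(π + d) = π + sd
- The other three cells: π
- Difference-in-differences: (π + sd − π) − (π − π) = sd

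A trend common to both arms is added to both second-round cells and cancels. The term sd does not.

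**3. Illustrative size of the shift.** The documents give neither s nor d, so both are assumptions.

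| s | d | shift sd |
|---|---|---|
| 10% | +30 points | +3 points |
| 20% | +30 points | +6 points |
| 30% | +30 points | +9 points |
| 10% | +10 points | +1 point |
| 30% | −10 points | −3 points |

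If s = 0 there is no bias.

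**4. The shift against sampling error.** With 300 per cell, 50% prevalence (assumed) and no clustering, SE = √(4 × 0.25/300) = 5.8 points, a 95% half-width of 1.96 × 5.8 = 11.3 points. With no true change, a 6-point shift raises the two-sided false-positive rate from 5% to about 18%, and a 9-point shift raises it to about 34%. Clustering, with three districts per arm, would widen the SE and lower these rates. The estimate would still be displaced by sd.

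**5. Penetration.** Assume 30% of other attenders were exposed and all campaign-driven attenders were. Exposure among current Arm 2 users is then s × 1 + (1 − s) × 0.30:

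- s = 10%: 0.10 + 0.90 × 0.30 = 37%
- s = 30%: 0.30 + 0.70 × 0.30 = 51%

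These are correct values for current users. They exceed the 30% among women who would have attended anyway.

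For FSW/AGYW generally, let e be true exposure and suppose exposed women are R times as likely to be in the frame. Observed exposure is eR/(eR + 1 − e). With e = 30% this is 34.9% (R = 1.25), 39.1% (R = 1.5) and 46.2% (R = 2). With R = 1 there is no overstatement.

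**6. Whether the plan handles it elsewhere.** Section 7.C describes adjustment for age and other individual characteristics for uptake, with a similar approach for secondary outcomes. Even if that covers the survey, age does not identify campaign-driven attenders. The second-round exposure questions do not either, since an established user may see an advertisement without attending because of it.

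**The case against.** The frame is defensible. Programme users are the trial population and the basis of the primary outcome, so surveying them is a natural way to explain uptake. Contact is partly set by team schedules, and both arms have peer educators and door-to-door outreach. The frame is wider than PrEP users, and champions work in venues the programme already serves, so many women they reach may already be in it. Champion and mobilisation activity lasts 6 months while the second survey follows a year of activity. If those activities began at launch (no start date is stated), they would have ended about six months before that survey. All of this could make s small, and it stands as a limit on size. None of it makes s zero, and the social media campaign itself runs for the full 12 months.

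The questionnaire is not in the documents, so a relevant item may exist. The described content does not show one.

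A reader might infer that penetration among the women served is overstated. The documents do not support that: women brought in by the campaign are women served, so the survey figure is valid for that group. Only the broader reading in Table 4, or a reading about women already in the programme before launch, is open to overstatement.

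The illustrative 3–9 points also lie within the unclustered 11.3-point half-width. That is a fair reason not to overrate the problem, but sampling error does not remove a systematic shift.

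**Conclusion.** The difference-in-differences on knowledge and attitudes is open to bias from a change in attendance confined to Arm 2, and nothing described in the plan detects or removes it. On assumed inputs (s of 10–30%, d of 30 points) the shift is 3–9 points with no true change. The real size is unknown because the documents contain no attendance response.

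A reader might go further and conclude that the survey results are biased, and upwards. The documents do not support that: the bias depends on attendance responding to the campaign, and newly drawn women could know less about PrEP than long-standing users.

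The point affects secondary and implementation outcomes. It leaves the primary uptake comparison untouched, since that uses programme data. It should be addressed because the remedy is cheap and the information cannot be recovered later.

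**What to change.** - **Survey items.** Add time since first programme contact to both rounds. Add what prompted first contact (advertisement or page, champion, mobilisation team, other) to the second round. A version without the campaign options can go in the first round if wanted.
- **Section 7.C.** Keep the full-sample difference-in-differences as the main survey analysis and describe its result as change among current attenders. Pre-specify a sensitivity analysis restricted, in both rounds, to women with at least 12 months since first contact. In the second round these are essentially women in the programme before launch.
- **Table 4.** Report penetration separately for established and newer users.
- **No gate.** Do not make attribution to the campaign depend on the sensitivity analysis. If one third of respondents qualified (an assumption), 100 per cell would give SE = √(4 × 0.25/100) = 10 points, and 80% power only for about (1.96 + 0.84) × 10 = 28 points before clustering. A pass/fail rule could suppress real effects.

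The cost is two survey items and one extra analysis, with no change to sites, sample size or recruitment. The established-user subset will be imprecise, relies on recall, leaves out the newer users a demand campaign aims to reach, and is still conditional on continued attendance, which the campaign may also affect. It reduces the problem but does not remove it.
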